#### 9.1.1 Dose Escalation

### 9.1.1.1 Dose Escalation Design

Dose assignment of subjects will be done using the improved mTPI design in order to determine the MTD of E7766. Each subject will be assigned a dose in accordance with the rules of the improved mTPI design based on a target dose-limiting toxicity (DLT) rate of 25% and its equivalence interval (EI) of 20% to 30%.

The dose assignment decision rule is pre-tabulated in (Table 1). Two subjects will be enrolled for each tested dose level, and recruitment to the dose level will be expanded as required per Table 1. Based on the number of subjects with DLTs in each dose level, dose assignment for the next dose will be determined according to the Table 2 after consultation between the investigators and the sponsors. For the lowest dose, extra subjects may be added if a DLT develops in 1 of the 2 subjects, if deemed appropriate. Subjects who are not evaluable for DLT (eg, those subjects who fail to complete at least 2 E7766 injections during

Eisai Confidential Page 51 of 138

Cycle 1 for reasons other than DLT occurrence) should be replaced within their dose level, if at least 2 subjects in total have not been tested at the dose level. Subject enrollment will be closed when the DLT rate at the lowest dose level greatly exceeds the target DLT rate (25%), or when the RP2D has been determined.

Additional details of the improved mTPI design are presented in Section 9.7.4.1.

[figure not shown]

Figure 3 Schematic for Dose Escalation

D = de-escalate to next lower dose, DLT = dose-limiting toxicity, E = escalate to next higher dose, MTD = maximum tolerated dose, RP2D = recommended Phase 2 dose, S = Stay at current dose.

Eisai Confidential Page 52 of 138

		Number of Subjects Treated at Current Dose					
		2	4	6	8	10	12
Number of Subjects With DLTs	0	Е	Е	Е	Е	Е	Е
	1	D a	S	Е	Е	Е	Е
	2	D, U	D	D	S	S	Е
	3		D, U	D	D	D	S
	4		D, U	D, U	D, U	D	D
	5			D, U	D, U	D, U	D
	≥6			D, U	D, U	D, U	D, U

Table 1 Decision Rule for Dose Assignment

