# 9.7.1.8 Tolerability/Safety Analyses

Evaluation of DLTs will be performed on the DLT Analysis Set. The number and percentage of subjects with DLT will be calculated.

All safety analyses will be performed on the Safety Analysis Set. Safety data, presented for each dose level/arm, total of each part, and overall as appropriate, will be summarized on an "as treated" basis using descriptive statistics (eg, n, mean, standard deviation, median, Q1, Q3, minimum, maximum for continuous variables; n [%] for categorical variables). Safety variables include treatment-emergent adverse events (TEAEs), clinical laboratory parameters, vital signs, 12-lead ECG results, ECOG performance status, and ECHO/MUGA scans. Study Day 1 for all safety analyses will be defined as the date of the first dose of study drug.

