# 9.7.4 Other Statistical/Analytical Issues

## 9.7.4.1 Improved Modified Toxicity Probability Interval Design in Dose Escalation Part

The improved mTPI design, which uses a Bayesian statistical framework and a beta-binomial hierarchical model, will be employed to determine the MTD and/or RP2D of E7766.

Decision rules for dose assignment will be based on the improved mTPI design with the target DLT rate of 25% and its equivalence interval (EI) of 20% to 30%, and a set of equal-width intervals as EI below/above EI (ie, below EI: 0% to 10%, 10% to 20%; above

Eisai Confidential Page 107 of 138

EI: 30% to 40%, ..., 90% to 100%). The posterior probabilities of each interval will be calculated with non-informative beta prior distribution Beta (1, 1). The location of the interval with the largest posterior probability—below EI, EI, or above EI—guides the decision for the next dose level to be assigned, ie, Dose Escalation (E), Staying at the current dose (S), or dose De-escalation (D), respectively. This dose assignment rule minimizes the posterior expected penalty in the Bayes' rule under a decision-theoretic framework with the equal prior expected penalties for E, S, and D. The entire dose assignment decision rule can be pre-tabulated as presented in Table 1.

The subject enrollment will be closed when the lowest dose has a >95% posterior probability of being above the target DLT rate of 25% (ie, an unacceptable DLT rate beyond the target DLT rate) or when the RP2D has been determined.

The MTD is defined as the dose with the smallest difference between the target DLT rate of 25% and an estimate of DLT rate at each dose among all the tested doses with a ≤95% posterior probability of being above the target DLT rate of 25%. The isotonically transformed posterior mean under the beta posterior distribution with non-informative beta prior distribution Beta (0.005, 0.005) will be used to determine the estimate of DLT rates at each dose. The pooled adjacent violators algorithm (PAVA) will be used to maintain monotonically the increase of DLT rate with increasing dose level. Late immune-related toxicities occurring after Cycle 1 (DLT period) and up to 90 days after last dose of E7766, will also be used to inform corrections to the MTD and aid selection of the RP2D.

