3.2.1 Dose Escalation

3.2.1.1 Dose Escalation Design

Dose assignment of subjects will be done using the improved mTPI (i.e mTPI-2) design in order to determine the MTD of E7766. Each subject will be assigned a dose in accordance with the rules of the mTPI-2 design based on a target dose-limiting toxicity (DLT) rate of 25% and its equivalence interval (EI) of 20% to 30%.

The dose assignment decision rule is pre-tabulated in the Decision Rule for Dose Assignment (Table 1). Dose assignment for the next dose will be determined according to the Method for Deciding the Dose of the Next Dose Group (Table 2) after consultation between the investigators and the sponsor. Subjects who are not evaluable for DLT should be replaced within their dose level, if at least 2 subjects in total have not been tested at the dose level. Subject enrollment will be closed when the DLT rate at the lowest dose level greatly exceeds the target DLT rate (25%) or when the RP2D has been determined.

Additional details of the mTPI-2 design are presented in [Section 5.3.6](#).

Table 1 Decision Rule for Dose Assignment

		Number of Patients																			
		1	2	3	4	5	6	7	8	9	10	11	12	13	14	15	16	17	18	19	20
0	E	E	E	E	E	E	E	E	E	E	E	E	E	E	E	E	E	E	E	E	
1	D	D	D	S	S	E	E	E	E	E	E	E	E	E	E	E	E	E	E	E	
2	DU *	D	D	D	D	S	S	S	S	E	E	E	E	E	E	E	E	E	E	E	
3		DU	DU	DU	D	D	D	D	S	S	S	S	S	E	E	E	E	E	E	E	
4			DU	DU	DU	DU	DU	DU	D	D	D	D	S	S	S	S	S	S	S	S	
5			DU	DU	DU	DU	DU	DU	D	D	D	D	D	D	D	S	S	S	S	S	
6			DU	D	D	D	D	D	D	D	D	D	D								
7			DU	D	D	D	D	D													
8			DU																		
9			DU																		
10			DU																		
11			DU																		
12			DU																		
13			DU																		
14			DU																		
15			DU																		

Number of Patients															
16												DU	DU	DU	DU
17												DU	DU	DU	DU
18												DU	DU	DU	
19												DU	DU		
20												DU			

Target DLT rate at MTD = 25% and its equivalence interval = 20% to 30%.

Display for more than 20 subjects at the current dose is omitted. If the required rules are not available in the table, the decision will follow the rule determined by the improved mTPI (i.e. mTPI-2) design with the same settings above.

Decision Table was calculated via East Bayes (EB 1.0.0).

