5.2 Study Subjects

5.2.1 Definitions of Analysis Sets

DLT Analysis Set is the group of subjects in the Dose Escalation part who have completed Cycle 1, without incurring certain major protocol deviations (for instance those related to dosing or others identified before database lock), with at least 2 E7766 injections during Cycle 1, and are evaluable for DLT, or subjects who have experienced DLT during Cycle 1. This will be the analysis set to evaluate tolerability.

Full Analysis Set is the group of subjects who received at least 1 dose of study drug. This will be the primary analysis set for efficacy evaluations, as well as for demographic and baseline characteristics.

Safety Analysis Set is the same group as Full Analysis Set. This will be the analysis set for all safety evaluations except DLT results.

Efficacy Analysis Set is the group of subjects who received at least 1 dose of study drug and had a baseline tumor assessment. This will be used for supportive analysis of ORR.

Pharmacodynamic Analysis Set and Pharmacokinetic/Pharmacodynamic Analysis Set are defined in separate PK or PK/PD analysis plan(s).

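### The dose-assignment table is entered by subjects treated, while DLTs are evaluated in DLT-evaluable subjects; read literally, an unreplaced non-evaluable subject counts as DLT-free

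*Protocol*

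**What the plan says.** - **Decision rule.** The columns of Protocol Table 1 are headed "Number of Subjects Treated at Current Dose", for 2, 4, 6, 8, 10 and 12 subjects. The synopsis table uses the same label. A note sends counts that are not displayed back to the underlying design.
- **Evaluability.** Protocol 9.1.1.2 and SAP 3.2.1.2 require at least 2 injections in Cycle 1, with an exception when treatment-related toxicity prevented more than one. A subject who received fewer than 2 because of E7766-related AEs goes to the Study Safety Committee as a potential DLT.
- **Replacement.** SAP 3.2.1.1, like Protocol 9.1.1.1 and 9.5.5, says that non-evaluable subjects "should be replaced within their dose level, if at least 2 subjects in total have not been tested at the dose level". It does not define what counts as tested.
- **Analysis population.** Under SAP 5.2.1 the "DLT Analysis Set is the group of subjects in the Dose Escalation part who have completed Cycle 1" and meet further conditions, or who had a DLT in Cycle 1. Protocol 9.7.1.8 says: "Evaluation of DLTs will be performed on the DLT Analysis Set".
- **Denominator of the posterior.** Protocol 9.7.4.1 and SAP 5.3.6 give the priors, the intervals and the 95% cut-off, but do not say which subjects make up n. SAP Table 1 tabulates every count from 1 to 20 and labels the axis simply as patients.

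**The concern.** The 25% target is a rate among subjects who could have shown a DLT. A level expanded to 4, 6 or more may hold subjects who left after one injection, for example through progression or withdrawal, and who need not be replaced. Entering Table 1 by treated count gives each of them the weight of a subject observed DLT-free through Cycle 1. That lowers the posterior DLT rate and can only move a decision towards staying, escalating or leaving a dose open to re-entry. The DLT percentage reported on the DLT Analysis Set could then differ from the count on which the dose decision was made. In a first-in-human, multi-site study, the operative table should not leave its denominator to inference.

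**Working it through.** **Inputs.** Protocol 9.1.1.1 and 9.7.4.1 give the target DLT rate of 25%, the equivalence interval of 20% to 30%, ten intervals of width 10%, a Beta(1,1) prior and cohorts of 2. The 95% cut-off is stated for closing the lowest dose and for MTD candidates; here it is applied to every cell to produce U. The documents give no rate of non-evaluability, so one and two such subjects per level (m = 1, 2) are assumptions.

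**Rule.** With x DLTs in n subjects the posterior is Beta(1+x, 1+n−x). The interval with the largest posterior probability decides: below 20% is E, 20–30% is S, above 30% is D. U is added if P(p > 0.25) > 0.95.

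**Plan's own table.** All 36 cells checked in Protocol Table 1 (n = 2 to 12, with the last row taken at 6 DLTs) are reproduced. The table is therefore right for whatever n is entered.

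**One non-evaluable subject.** There are 2+4+6+8+10+12 = 42 combinations of treated count and DLTs. Three change:

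| Treated / evaluable | DLTs | By treated | By evaluable |
|---|---|---|---|
| 4 / 3 | 1 | S | D |
| 6 / 5 | 1 | E | S |
| 6 / 5 | 3 | D | D,U |

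- 1 DLT in 6: under Beta(2,6), the 10–20% interval has 0.274 and the 20–30% interval 0.247, so E.
- 1 DLT in 5: under Beta(2,5), F(x) = 1 − (1−x)^6 − 6x(1−x)^5, so F(0.1) = 0.114, F(0.2) = 0.345, F(0.3) = 0.580 and F(0.4) = 0.767. The first four intervals have 0.114, 0.230, 0.235 and 0.187, so S.
- 1 DLT in 4: under Beta(2,4), 20–30% has 0.209 and 30–40% has 0.191, so S. 1 DLT in 3: under Beta(2,3), F(x) = 1 − (1−x)^4 − 4x(1−x)^3 gives 0.168 for 20–30% and 0.177 for 30–40%, so D.
- 3 DLTs in 6: P(p > 0.25) = 0.929, so D without U. 3 DLTs in 5: P(p > 0.25) = P(Bin(6, 0.25) ≤ 3) = 0.1780 + 0.3560 + 0.2966 + 0.1318 = 0.9624, so U is added.

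**Two non-evaluable subjects.** Of 3+5+7+9+11 = 35 combinations, nine change:

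| Treated / evaluable | DLTs | By treated | By evaluable |
|---|---|---|---|
| 4 / 2 | 1 | S | D |
| 4 / 2 | 2 | D | D,U |
| 6 / 4 | 1 | E | S |
| 6 / 4 | 3 | D | D,U |
| 8 / 6 | 2 | S | D |
| 10 / 8 | 4 | D | D,U |
| 12 / 10 | 2 | E | S |
| 12 / 10 | 3 | S | D |
| 12 / 10 | 5 | D | D,U |

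In all twelve changed cells the treated count gives the less cautious decision.

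**Probability of a changed decision** (exact binomial in the evaluable subjects):

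- 6 treated / 5 evaluable, escalate. The treated count needs X ≤ 1 of 5; the evaluable count needs X = 0. At p = 0.25: 0.75^5 + 5(0.25)(0.75^4) = 0.2373 + 0.3955 = 63.3%, against 23.7%. At p = 0.40: 0.0778 + 0.2592 = 33.7%, against 7.8%.
- 4 treated / 3 evaluable, no de-escalation, at p = 0.40: 0.216 + 0.432 = 64.8%, against 21.6%.
- 12 treated / 10 evaluable, escalate: 52.6% against 24.4% at p = 0.25, and 16.7% against 4.6% at p = 0.40.

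With one non-evaluable subject, the probability of escalating is the same under both counts at every even treated count from 2 to 12 except 6.

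**The case against.** The strongest reply is that evaluable counts were intended. The plan defines evaluability, makes the DLT Analysis Set the set for tolerability, and never says in terms that a non-evaluable subject is counted as DLT-free. A reader might infer such an explicit instruction from the Table 1 heading, but the documents do not contain one. What stands is that the only stated label in the protocol table and synopsis is subjects treated, and nothing overrides it.

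The note on counts not displayed also gives some cover. A replacement in the first cohort makes the treated count odd, Table 1 has no such column, and the underlying rule then applies. It would be wrong to say that the note can never operate. It still does not direct anyone with 4 treated and 3 evaluable to use 3, because the column for 4 exists. SAP Table 1 permits entry by evaluable count without requiring it.

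Two safeguards narrow the gap. Dropout caused by E7766-related AEs goes to the Study Safety Committee, so the exposure is mainly to dropout for other reasons. The investigators and sponsor also consult before each dose assignment, so the table is not applied mechanically. At the first cohort of 2, replacement largely removes the problem if tested means evaluable.

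Finally, SAP section 7 says that escalation ended early and no MTD was determined, and SAP 3.2.2 says that no expansion subjects will be enrolled. Relabelling now changes no past decision.

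**Conclusion.** The point holds as an unreconciled denominator in the primary decision rule. Its literal reading errs in one direction only. The effect is confined to a few cells (3 of 42 with one unreplaced non-evaluable subject, 9 of 35 with two), but several of these fall at 4 and 6 treated, early in any expanded level, and there the change in decision probability is large. A switch to Escalate occurs only at 1 DLT in 6 treated, or at 2 DLTs in 12 treated with two non-evaluable.

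The result rests on assumed numbers of non-evaluable subjects and on non-evaluability being unrelated to DLT risk. If those subjects would all have been DLT-free, the treated count would not be biased.

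A reader might go further and infer that the trial will select too toxic an MTD. The documents do not support that. No MTD was determined, the plan gives no non-evaluable rate or dose-toxicity curve, and it does not say that the MTD estimate would use treated n. What is affected is the dose-assignment decisions and how well they match the reported DLT percentages.

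**What to change.** 1. Label the axis of Table 1 in Protocol 9.1.1.1, the synopsis and the SAP as DLT-evaluable subjects at the current dose.
2. State in Protocol 9.7.4.1 and SAP 5.3.6 that n in the interval decision, the 95% rule and any DLT-rate estimate counts only subjects who are DLT-evaluable under Protocol 9.1.1.2, and say whether tested in the replacement rule means the same.
3. Add to the protocol table the odd-numbered columns that the SAP table already carries. The stated settings give, for example, D for 1 DLT in 3, S for 1 in 5, and S for 2 in 7 or 2 in 9.
4. In the abbreviated CSR, list treated and evaluable n beside each dose decision and flag any decision that would differ. With escalation closed, this step matters most.

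The cost is wording in three tables, a sentence in each of two sections and one short listing; the mTPI-2 settings do not change. The downside for any further escalation under this rule is that a cohort with a non-evaluable subject is decided on a smaller n, so some levels may need another cohort.

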Target DLT rate at MTD = 25% and its equivalence interval = 20% to 30%, Cohort size = 2 subjects. Display for more than 12 subjects at the current dose is omitted. If the required rules are not available in the table, the decision will follow the rule determined by the improved mTPI design with the same settings above. E = Escalate to the next higher dose, S = Stay at the current dose, D = De-escalate to the next lower dose, U = Current dose is unacceptably toxic (ie, Do not re-enter the current dose).

DLT = dose-limiting toxicity, MTD = maximum tolerated dose, mTPI = modified toxicity probability interval. a: Extra subjects may be added for the lowest dose, for example if the investigators and the sponsor determine that more subjects would be required to adequately evaluate that dose level and it is considered safe to do so.

Subjects will be assigned to a dose level in the order of study entry. There should be at least 7 days between initiating treatment of the first and second subject in each new dose escalation. This would provide enough safety margin in terms of safety evaluation for any acute serious toxicities arising from activation of the immune system, which would generally be expected to occur within the first hours or 1 to 3 days of drug exposure. In cohorts where the dose is de-escalated or re-escalated, a delay in administration between the first subject and subsequent subjects in that cohort is not required if the same or a higher dose level has already been investigated in a previous cohort.

The first E7766 dose administered to the subjects will be 75  $\mu g$  (refer to Section 9.2 for justification of starting dose). The dose of subsequent dose groups will be determined based on the E7766-related AEs that develop in subjects in the prior dose group during the 3 weeks of Cycle 1 (see Table 2). When escalating or de-escalating the dose to the next dose level according to the improved mTPI design, if there is a higher or lower dose level that has been tested previously, subjects should be enrolled to the previously tested dose and Table 2 below shall not apply. In addition, intermediate doses can be further added if necessary based on the safety or PK of the previously tested dose. The addition of new dose levels will be decided based on discussions between the investigators and sponsors during dose escalation meetings.

Eisai Confidential Page 53 of 138

Table 2	Method for Deciding the Dose of the Next Dose Group
---------	---

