Dose Escalation Steps	E7766-Related Toxicity During Cycle 1
Increase ~75% to 100%	Up to Grade 1
Increase ~30% to 60%	Grade 2 in 1 subject
Increase ~10% to 30%	Grade 2 in 2 or more subjects and/or
	Grade 3 or higher in 1 or more subject

Intrapatient dose escalation of study drug will be allowed in the study after a minimum of 3 cycles of study therapy at the designated dose and after there is sufficient information to ensure safety at the higher dose. The decision for individual cases, if requested, will be made in agreement between the investigators and the sponsor. Subjects on the intrapatient dose escalation will be identified, but included in the evaluation of tolerability/safety and efficacy at the dose level assigned in Cycle 1, instead of at the higher dose level.

Late immune-related toxicities occurring after Cycle 1 (DLT period) and up to 90 days after last dose of E7766, will also be considered to inform any corrections to the MTD and aid selection of the RP2D.

Escalation of E7766 dose will be achieved based on the concentrations and volumes administered according to the guidance in Table 3.

During the Dose Escalation part, selected dose level cohorts may accrue additional subjects to provide additional safety, drug administration-related, biomarker, and/or PK data needed for selection of the RP2D.

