5.3.6 Other Considerations

Improved Modified Toxicity Probability Interval Design (mTPI-2) in Dose Escalation Part

The mTPI-2 design, which uses a Bayesian statistical framework and a beta-binomial hierarchical model, will be employed to determine the MTD and/or RP2D of E7766.

Decision rules for dose assignment will be based on the mTPI-2 design with the target DLT rate of 25% and its equivalence interval (EI) of 20% to 30%, and a set of equal-width intervals as EI below/above EI (ie, below EI: 0% to 10%, 10% to 20%; above EI: 30% to 40%, ... , 90% to 100%). The posterior probabilities of each interval will be calculated with non-informative beta prior distribution Beta (1, 1). The location of the interval with the largest posterior probability—below EI, EI, or above EI—guides the decision for the next dose level to be assigned, ie, Dose Escalation (E), Staying at the current dose (S), or dose De-escalation (D), respectively. This dose assignment rule minimizes the posterior expected penalty in the Bayes' rule under a decision-theoretic framework with the equal prior expected penalties for E, S, and D. The entire dose assignment decision rule can be pre-tabulated as presented in [Table 1](#).

The subject enrollment will be closed when the lowest dose has a >95% posterior probability of being above the target DLT rate of 25% (ie, an unacceptable DLT rate beyond the target DLT rate) or when the RP2D has been determined.

The MTD is defined as the dose with the smallest difference between the target DLT rate of 25% and an estimate of DLT rate at each dose among all the tested doses with a $\leq 95\%$ posterior probability of being above the target DLT rate of 25%. The isotonically transformed posterior mean under the beta posterior distribution with non-informative beta prior distribution Beta (0.005, 0.005) will be used to determine the estimate of DLT rates at each dose. The pooled adjacent violators algorithm (PAVA; [Bartholomew et al., 1983](#)) will be used to maintain monotonically the increase of DLT rate with increasing dose level. Late immune-related toxicities occurring after Cycle 1 (DLT period) and up to 90 days after last dose of E7766, will also be used to inform corrections to the MTD and aid selection of the RP2D.

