7 CHANGES IN THE PLANNED ANALYSES

MTD is not determined due to early termination of dose escalation part. As no subjects will be enrolled for dose expansion part, analysis for expansion arm will not be conducted.

There will be an abbreviated CSR, the following analysis planned will be removed:

- Protocol deviations
- Medical history and Prior and concomitant medications
- ECOG
- Listings for tumor assessment
- Efficacy analysis for efficacy analysis set
- MUGA or Echocardiogram

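### A U flag closes only the flagged dose, so a higher tested dose stays a candidate and can occasionally be named MTD

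*Protocol*

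**What the plan says.** - **Closure flag.** The Table 1 notes (Protocol 9.1.1.1; same note in SAP 3.2.1.1) read "U = Current dose is unacceptably toxic (ie, Do not re-enter the current dose"). No note extends this to higher doses.
- **Enrollment stop.** Protocol 9.7.4.1: "The subject enrollment will be closed when the lowest dose has a >95% posterior probability of being above the target DLT rate of 25" per cent, or once the RP2D is set. This is the only place where a flag at one dose closes others.
- **MTD.** SAP 5.3.6: "The MTD is defined as the dose with the smallest difference between the target DLT rate of 25% and an estimate of DLT rate". Candidates are screened one by one; Protocol 9.7.4.1 refers to "an estimate of DLT rate at each dose among all the tested doses with a ≤95" per cent posterior probability of exceeding 25%.
- **Monotonicity.** Protocol 9.7.4.1: "The pooled adjacent violators algorithm (PAVA) will be used to maintain monotonically the increase of DLT rate with increasing dose level".
- **Optional accrual.** Protocol 9.1.1.1: "selected dose level cohorts may accrue additional subjects to provide additional safety, drug administration-related, biomarker, and/or PK data". There is no exception for doses above a flagged one.
- **Link to RP2D.** Protocol 9.1.1.3 makes the MTD the ceiling for the RP2D.
- **Status.** SAP 7: "MTD is not determined due to early termination of dose escalation part".

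**The concern.** If the DLT rate cannot fall with dose, strong evidence that dose B exceeds 25% is at least as strong evidence against dose C above it. The plan follows that logic for the lowest dose, where a flag ends enrollment, and in the isotonic estimate. It does not follow it for a flag at any other dose, or for the list of MTD candidates. If B is flagged after C has already been tested, C stays open to optional accrual and stays eligible as MTD as long as its own data, possibly from few subjects, do not cross 95%. The RP2D ceiling in a first-in-human study could then lie above a dose closed as unacceptably toxic.

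**Working it through.** **Inputs.** From the Table 1 notes: "Target DLT rate at MTD = 25% and its equivalence interval = 20% to 30%, Cohort size = 2 subjects". From Protocol 9.7.4.1: Beta(1,1) prior and 10%-wide intervals for decisions; Beta(0.005, 0.005) prior and PAVA for the MTD estimate. From Protocol 9.7.2: about 35 subjects and about 10 dose levels.

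**Formulas.** With x DLTs in n subjects:
- The decision is set by the interval with the most mass under Beta(1+x, 1+n−x).
- U applies when P(p > 0.25) > 0.95 under the same posterior.
- The MTD estimate is (x+0.005)/(n+0.01), pooled by PAVA with weights n. The MTD is the eligible dose closest to 0.25.

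**Plan's own figure.** These rules reproduce all 36 filled cells of Protocol Table 1.

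**Example 1 (22 subjects).** Every step is a Table 1 decision:

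| Step | Dose, cumulative DLTs/n | Decision |
|---|---|---|
| 1 | A 0/2 | E |
| 2 | B 0/2 | E |
| 3 | C 1/2 | D |
| 4 | B 0/4 | E |
| 5 | C 2/4 | D |
| 6 | B 0/6 | E |
| 7 | C 2/6 | D |
| 8 | B 2/8 | S |
| 9 | B 4/10 | D |
| 10 | A 0/4 | E |
| 11 | B 6/12 | D,U |

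- P(p > 0.25): A 0.237, B 0.976 (excluded), C 0.756 (eligible).
- Unpooled estimates: A 0.005/4.01 = 0.0012; B 6.005/12.01 = 0.5000; C 2.005/6.01 = 0.3336.
- B exceeds C, so PAVA pools them: (12 × 0.5000 + 6 × 0.3336)/18 = 0.4445.
- Distances from 0.25: A 0.2488, C 0.1945. **C is named MTD.** If PAVA uses eligible doses only, C stays at 0.3336 and is still chosen.

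**Example 2 (18 subjects).** A 0/2 E; B 0/2 E; C 1/2 D; B 0/4 E; C 1/4 S; C 2/6 D; B 2/6 D; A 0/4 E; B 4/8 D,U. B has P = 0.951. Pooled B and C: (8 × 0.5000 + 6 × 0.3336)/14 = 0.4287, distance 0.179. C is again named.

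**Prior for the 95% MTD screen.** It is not stated separately. Under Beta(0.005, 0.005), 6/12 gives 0.966 and Example 1 stands; 4/8 gives 0.930 and Example 2 does not.

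**Frequency.** The true curves are assumptions: five 10-level curves, 36 subjects, cohorts of 2, 60,000 trials each.
- Steady: .03 .06 .10 .15 .20 .25 .32 .40 .48 .56
- Early: .05 .12 .20 .28 .36 .44 .52 .60 .68 .75
- Flat: .10 .15 .20 .24 .27 .30 .32 .34 .36 .38
- Plateau: .15 .22 .28 .30 .32 .34 .36 .38 .40 .42
- Late: .01 .02 .03 .05 .08 .12 .18 .25 .35 .45

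| Outcome (% of trials, range over curves) | Closed dose blocks E | E may pass over it to a tested dose |
|---|---|---|
| Eligible tested dose above a U dose | 2.0–4.8 | 1.8–3.8 |
| MTD above a U dose, PAVA on all tested doses | 0.12–0.23 | 0.41–0.95 |
| MTD above a U dose, PAVA on eligible doses only | 0.22–0.54 | 0.71–1.73 |

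A second set of eight assumed curves (6 or 10 doses, caps of 24 and 36) gave higher rates. Leaving out trials where the lowest dose was the flagged one, and applying PAVA to all tested doses, the largest rate was 3.16% − 0.01% = 3.15%. That came from a curve jumping from .05 to .35 and then nearly flat, with pass-over and 36 subjects.

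**Lowest-dose variant, counted separately.** With the lowest dose at 4/6 (P = 0.987) and the next at 1/2 (P = 0.844), enrollment closes for toxicity. The next dose is then the only eligible one, with a pooled estimate of 0.625.

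**The case against.** - **C may not really be open.** After B closes, E from A points to B, so on a strict reading Table 1 gives no route back to C. This stands, and it is why the blocking rate is the lower one. C nevertheless remains an MTD candidate and available for optional accrual.
- **The examples are fragile.** B goes from 0 DLTs in 6 to 6 in the next 6 (Example 1), or from 0 in 4 to 4 in 4 (Example 2). One later DLT at A, for instance 1/6 with estimate 0.167, would make A the MTD. This is true and supports calling the event uncommon. Further DLT-free subjects at A would not change the outcome.
- **The fix may close doses wrongly more often than it helps.** A dose flagged by chance (true rate at most 25%) with an eligible tested dose above it occurs in 0.8–1.5% of all trials, more often than the 0.12–0.23% it prevents on the blocking reading. The count stands. But on that reading Table 1 would not return to the higher dose anyway, and the plan already accepts this kind of cost at the lowest dose.
- **Safeguards and cited design papers.** Joint investigator and sponsor review, intermediate doses and late-toxicity review could catch the problem, and the cited papers, not available here, may treat it. Nothing in either document requires the higher dose to be excluded, and the MTD is defined by formula.
- **No consequence in this trial.** Correct: no MTD was determined and no expansion subjects will be enrolled.

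**Conclusion.** The concern holds. As written, the rules can close a dose as unacceptably toxic and name a higher one as MTD, against the monotone assumption the plan itself uses. The event is uncommon: roughly 0.1–1% of trials on the five assumed curves with PAVA on all tested doses, and up to 1.7% with PAVA on eligible doses only. Less gradual curves gave about 3%. The size rests on assumed curves and on two points the documents leave open: whether E may pass over a closed dose, and which doses enter PAVA. Example 1 depends on neither, nor on which of the two stated priors is used for the 95% screen. The defect lies in the written safety rule and affects no reported result.

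**What to change.** Change two sentences in the protocol and the same two in the SAP.

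1. **Table 1 note:** U bars the flagged dose and every higher dose, whether by Table 1 assignment, optional accrual or intrapatient escalation. Intermediate doses below the flagged dose remain allowed.
2. **MTD definition (Protocol 9.7.4.1, SAP 5.3.6):** candidates are the tested doses below the lowest dose that exceeds the 95% cut, or all tested doses if none does. In the same sentence, state that PAVA uses all tested doses.

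An MTD above a flagged dose then becomes impossible by construction. Both examples would give A instead of C, and the lowest-dose variant would give no MTD. Table 1 cells, the 25% target and the 95% threshold stay as they are, and no extra subjects or data are needed.

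The cost is that doses above one flagged by chance can no longer be explored. On the five assumed curves, the flagged dose truly has a rate of at most 25% in 19–57% of the affected trials, or 0.8–1.5% of all trials.
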